# 4.2. **Prior Clinical Experience**

### 4.2.1. Clinical Study Overview

To date, a total of 11 clinical trials have been conducted with MN-001 and over 600 subjects have been dosed. Doses of MN-001 ranging from 80 mg to 2000 mg for up to 12 weeks in 6 Phase 1 studies, 4 Phase 2 studies and 1 Phase 3 study have been studied in healthy subjects and patients with asthma and interstitial cystitis. A summary of completed studies is listed in Table 3.

### Phase 1 Studies

In the single dose studies of 80 mg to 600 mg, there appeared to be few adverse events. The most common treatment emergent adverse events (TEAEs) were mild diarrhea, sensation of borborygmus, and heavy headedness. No clinically significant changes in vital signs, ECGs, and safety labs were observed.

In two multiple dose studies (study KCA-757 and study 478-02), MN-001 250 mg to 1000 mg bid was administered for approximately 7 days in healthy volunteers and subjects with mild bronchial hypersensitivity. No serious adverse events were reported and no subjects discontinued the study due to an adverse event. The most common AEs experienced in study 478-02 were upper abdominal pain (reported by 1 subject each in the 500 mg and 750 mg groups), loose stools (reported by 1 subject each in the 500 mg and 1000 mg groups), and nausea (reported by 1 subject each in the 750 mg and 1000 mg groups). The Investigator considered the following treatment-emergent AEs to be possibly or probably related to study drug (treatment group in parentheses): abdominal pain (placebo), upper abdominal pain (500 mg and 750 mg), dyspepsia (1000 mg), fatigue (placebo), loose stools (500 mg and 1000 mg), nausea (750 mg and 1000 mg), somnolence (750 mg), urine odor abnormal (500 mg).

In study 478-02, vital signs were within normal limits. All mean ECG measurements remained within normal limits. At Hour 359.67 mean QTc for the 750 mg group increased 27.66 ms from baseline for a mean QTc of 395.83 ms and mean heart rate increased 14.50 bpm from baseline for a mean heart rate of 70.67 ms. No other marked mean changes from baseline were noted. The Investigator did not consider any of the ECG abnormalities in this study to be adverse events.

All treatment groups, including the placebo group, exhibited notable mean increases in CPK (ranging between 22 to 135 U/L) at Hour 360. No other marked mean changes from baseline were noted for the remaining serum chemistry parameters.

### High Doses of MN-001 (1500 mg)

Study MN-001-CL-003 was another multiple dose study in healthy volunteers testing doses of 1500 mg for 5 days. In this study, no SAEs occurred and no subjects discontinued the study due

to a TEAE. Two subjects reported a TEAE during the study. Both subjects experienced dizziness (mild, possibly related), one on Day 2 and the other on Day 3 of dosing with MN-001 750 mg bid.

Mean serum chemistry and hematology results showed transient fluctuations between screening and follow-up on Day 11, 8 hours after the last dose, but no apparent treatment-related trends were observed for any of the serum chemistry or hematological parameters evaluated. None of the abnormal laboratory values observed during the study was considered a clinically significant treatment-related change, and no AEs related to abnormal laboratory values were reported. No clinically significant changes in vital sign parameters and ECGs were noted during the study.

The mean triglyceride (mg/dL) changes from baseline at Day 11 are listed below.

Time point	MN-001 1500 mg/day			
	(N=11)			
Screening	145.4			
Day 11	87.5			
	(-39.8%)			

# Phase 2 Studies

### Study KCA-757-T201

MN-001 100 mg, 200 mg, 400 mg and 600 mg was evaluated in 112 asthma patients over 6 weeks. No serious adverse events occurred and 11 subjects discontinued due to a TEAE. Seven subjects experienced 20 adverse reactions.

### Study MN-001-CL-001

MN-001 (500 mg tid, 750 mg bid, or 750 mg qd) or placebo was evaluated for 4 weeks in 147 asthma patients. AEs within the Gastrointestinal Disorders system organ class were the most commonly observed, reported by 18.2% of the combined MN-001 subjects and 10.8% of those receiving placebo. These AEs appeared to demonstrate a dose relationship, and the most frequent AEs among the combined MN-001 treatment groups were diarrhea, nausea, and vomiting. Each of these individual events occurred in less than 10% (with only diarrhea exceeding 5%) of all MN-001-treated subjects. No severe gastrointestinal AEs were reported, and none led to discontinuation from the study.

The mean triglyceride (mg/dL) changes from baseline at Week 4 are listed below.

Time point	Placebo (N=36)	500mg tid (N=36)	750mg bid (N=36)	750mg qd (N=36)
Screening	132.3	109.5	125.5	112.2
Week 4	126.9 (-4.1%)	91.6 (-16.3%)	98.5 (-21.5%)	117.2 (+4.5%)

### Study MN-001-CL-002

MN-001 500 mg bid and 500 mg qd were evaluated in 305 patients with interstitial cystitis. The TEAE most frequently reported by all the patients in the MN-001 group was diarrhea, which was higher in both MN-001 groups compared with placebo and higher in the MN-001 500 mg bid group compared with the MN-001 500 mg qd group. Although the incidence of loose stools was lower than the incidence of diarrhea, similar comparisons as seen with diarrhea among the treatment groups were also observed for loose stools.

The mean triglyceride (mg/dL) changes from baseline at Week 4 are listed below.

Time point	Placebo	500mg qd	500mg bid
	(N=100)	(N=94)	(N=106)
Baseline	144.3	136.1	135.7
Week 4	144.5	109.5	106.7
	(+0.1%)	(-19.5%)	(-21.3%)

### Phase 3 Study

MN-001 (500 mg tid or 750 mg bid) or placebo was evaluated for 12 weeks in patients with asthma. This study was stopped early by sponsor in June 2007 due to strategic reasons unrelated to the safety or efficacy of study drug. (MediciNova, Inc.'s business decision to discontinue further development of MN-001 in its current immediate-release formulation for asthma indication was based on the competitive landscape at that time.)

There were total 154 subjects enrolled, 152 subjects were randomized (108 in MN-001 groups and 44 in placebo group). The study was terminated before planned enrollment was achieved. In the all MN-001 groups, the system organ class (SOC) categories with the most reported TEAEs were gastrointestinal disorders (19% vs. 5% in the placebo group), infections and Infestations (11% vs. 18% in the placebo group) and respiratory, thoracic and mediastinal disorders (8% vs. 7% in the placebo group). In the placebo group, the SOC category with the most reported TEAEs

MEDICINOVA, INC.

CONFIDENTIAL

(incidence of  $\geq 10\%$ ) was infections and infestations (18%). The only AE that was reported in > 2 subjects in each treatment group was diarrhea, which occurred at a higher frequency in the 750 mg bid group than the 500 mg tid group (21% vs. 9% respectively). The TEAEs experienced by > 2 subjects in the all MN-001 group were nasopharyngitis (4%), urinary tract infection (3%), asthma (3%), and joint sprain (3%).

The mean triglyceride (mg/dL) changes from baseline at Week 4 are listed below.

Time point	Placebo	500 mg tid	750 mg bid	
	(N=44)	(N=54)	(N=53)	
Baseline	135.4	159.4	117.0	
Week 4	123.1 (-9.1%)	112.5 (-29.4%)	94.1 (-19.6%)	

Additional safety information is reported in the Investigator Brochure.

# Table 3:Clinical Studies

Phase	Study Number	Title	Design	Dosage	Treatment Duration	Target Population	# of Subjects Enrolled
1	2254	Ascending dose tolerance study of KCA-757 (MN- 001) in healthy volunteers with preliminary pharmacokinetic assessment	Open-label, single- dose	80 mg, 160 mg	single-dose	Healthy Volunteers	5
1	151408	The disposition of 14C- KCA-757 (MN-001) in man	Open-label, single oral dose to investigate the rates and routes of excretion and the plasma kinetics of total radioactivity following [  C]- KCA-757 (MN- 001)	80 mg	single-dose	Healthy Volunteers	4
1	Kyorin	Phase 1 Trial of KCA-757 (MN-001) Single-dose study	Ascending, single- dose to evaluate safety and PK	100 mg to 600 mg	single-dose	Healthy Volunteers	29
1	Kyorin	Phase 1 Trial of KCA-757 (MN-001) Repeated-dose study	Safety and PK	300 mg bid	7 days	Healthy Volunteers	6
1	478-02	A Randomized, Double- Blind, Placebo-Controlled, Ascending Dose Study to Assess the Safety and Tolerability of MN-001 When Given in Multiple Doses to Healthy Volunteers and the Pharmacodynamic Effect of MN-001 When Given in Multiple Doses to Volunteers with Mild Bronchial Hypersensitivity	Randomized, double-blind safety and tolerability	250, 500, 750, 1000 mg bid	6 days	Healthy Volunteers and bronchial hypersensiti ve subjects	32
1	MN- 001-CL- 003	A Phase I, Randomized Single-blind study to Determine the Relative Pharmacokinetics of Two Dosing Regimens of MN- 001 Administered Orally to Normal, Healthy Male and Female Subjects	Single-Blind, Randomized 1:1, Crossover	500mg tid and 750mg bid	5 days of dosing for each regimen	Healthy Volunteers	11 subjects randomized and completed
2	KCA- 757- T201	Early Phase 2 Study of KCA-757 (MN-001)	Open-label	50 mg bid, 100 mg bid, 200 mg bid, 300 mg bid	6 weeks	Bronchial asthma	108 subjects
2	4204	A standard antigen challenge study of KCA- 757 (MN-001) in 10	Cross-over	300 mg bid	single-dose	Asthma	3

Phase	Study Number	Title	Design	Dosage	Treatment Duration	Target Population	# of Subjects Enrolled
		patients with asthma					
2	MN- 001-CL- 001	A Randomized, Double- Blind, Placebo-Controlled Study Evaluating the Effects of MN-001 in Subjects with Mild to Moderate Asthma	Double-Blind, Randomized	500mg tid, 750mg bid, 750mg qd, or placebo	4 weeks	Mild to Moderate Asthma pts	147 subjects randomized with 131 completing, placebo N=37, 500mg tid N=37, 750mg bid N=37, 750mg qd N=36
2	MN- 001-CL- 002	A Phase II, Randomized, Double-blind, Placebo- Controlled Multi-Center Study to Evaluate the Efficacy and Safety of Two Dosing Regimens of MN- 001 in Patients with Interstitial Cystitis	Double-Blind, Randomized 1:1:1	500mg bid 500mg qd, or placebo	8 weeks	Interstitial Cystitis pts	305 subjects randomized with 251 completing, placebo N=102, 500mg qd=95, 500mg bid N=108
3	MN- 001-CL- 004	A Randomized, Double- Blind, Placebo-Controlled Study Evaluating the Effects of MN-001 in Subjects with Mild to Moderate Asthma	Double-Blind, Randomized 1:1:1	500mg tid 750mg bid, or placebo	12 weeks	Mild to Moderate Asthma pts	152 subjects randomized 108 MN-001 44 Placebo

# 4.3. **Potential Drug-Drug Interactions**

From the *in vitro* CYP enzyme study, both MN-001 and MN-002 were found to be highly bound to human serum albumin.

- MN-001 and MN-002 directly inhibit CYP2C enzymes in a Michaelis-Menten manner, and do so with a relatively high degree of potency according to the following rank order: CYP2C8 > CYP2C9 > CYP2C19. The IC50 values for MN-001 and MN-002 are 1.5 and 1.4 μM for CYP2C8; 3.8 and 8.1 μM for CYP2C9; and 25 and 28 μM for CYP219, respectively. As an inhibitor of these CYP2C enzymes, MN-001 tended to be slightly more potent than MN-002 and neither compounds exhibited evidence of metabolism- or time-dependent inhibition of CYP2C8, CYP2C9 or CYP2C19.
- MN-001 and MN-002 directly inhibited several CYP enzymes (CYP1A2, CYP2A6, CYP2B6, CYP2D6, CYP2E1 and CYP3A4/5) in a non-Michaelis-Menten manner whereby they caused little or no inhibition up to a certain concentration, after which they caused marked inhibition of these CYP enzymes by an unknown mechanism.

Based on data from single and repeat oral dose PK study, with the proposed dose of MN-001 250 mg/day (250 mg qd), plasma concentrations may peak at ~ 575 ng/ml (~ 1.1  $\mu$ M) for MN-001 and ~ 5200 ng/mL (~ 9.8  $\mu$ M). These results suggest that MN-001 and MN-

002 could potentially inhibit the metabolism of concomitantly administered drugs, particularly the concomitant drugs that are substrates of CYP2C8 and CYP2C9.

# 5. TRIAL OBJECTIVES AND PURPOSE

This is a multi-center, proof-of-principle, open-label study designed to evaluate the efficacy, safety, and tolerability of MN-001 in non-alcoholic steatohepatitis (NASH) and non-alcoholic fatty liver disease (NAFLD) subjects with hypertriglyceridemia.

# 5.1. Primary Objectives

The primary objectives of the study are:

- To evaluate the effects of MN-001 on Cholesterol Efflux Capacity in NASH and NAFLD subjects with hypertriglyceridemia
- To evaluate the effects of MN-001 on triglyceride levels in NASH and NAFLD subjects with hypertriglyceridemia

# 5.2. Secondary Objectives

The secondary objectives are:

- To evaluate the safety and tolerability of MN-001
- To evaluate PK profile of MN-001/MN-002
- To evaluate the effect of MN-001 on Lipid profile
  - HDL-C, LDL-C, Total cholesterol level
- To evaluate the effect of MN-001/002 on liver enzymes
- To evaluate the effect of MN-001/002 on the percentage of fat in the liver assessed using MRI at Week 12

# 6. OVERALL STUDY DESIGN AND PLAN: DESCRIPTION

The study will consist a Screening Phase (up to 4 months) followed by a Treatment Phase (12 weeks), and a Follow-up visit (within 1 week after the last dose).

A total of 40 male and female subjects  $\geq 18$  years of age are planned to be enrolled.

The study phases are described below and displayed in Figure 1 and the Schedule of Assessments is displayed in Table 1.

### Figure 1: Study Design

# 6.1. Screening Phase (up to - 4 months to - 7 days)

A total of up to 4 months will be allowed to complete the screening assessments. During the Screening Phase, subjects will be assessed for study eligibility. After signing the informed consent form, the following assessments will be performed: medical history including review of prior and current medications, physical examination including height and body weight, waist circumference, vital signs and an electrocardiogram. Clinical labs, routine chemistries (including CPK, liver enzymes and fasting lipid profile), hematology, coagulation profile, urinalysis and a serum pregnancy test will be collected as well as cytokeratin-18 (CK-18), a biomarker for NASH diagnosis. An alcohol consumption questionnaire will be administered and a MRI scan of the liver will be performed. Serum fibrosis markers, the Fib-4 index (age, AST, ALT, PLT) and NAFLD fibrosis score (age, BMI, AST/ALT ratio, IFG/DM, PLT, Albumin) will be calculated.

Detailed information on permitted and excluded concomitant medications is provided in Section 8.2 and Section 8.3 of the protocol.

# 6.1.1. Diagnosis at Screening

Subjects must have a histologically confirmed diagnosis of NASH (NAS of  $\geq$  3 with at least 1 point being ballooning) by liver biopsy within the past 36 months or NAFLD confirmed by imaging studies. The diagnosis must be noted in the source documents and a copy of the report must be obtained.

### 6.1.2. Treatment Phase

Subjects who complete all of the screening assessments will repeat laboratory tests around 1 week prior to Treatment Day 1 (Baseline) to confirm their eligibility. Subjects who continue to be eligible will return to the clinic on Treatment Day 1 (Baseline) and be enrolled to receive MN-001 250 mg qd for 4 weeks and will take MN-001 250 mg bid (500 mg) for 8 weeks. Subjects will receive MN-001 for a total of 12 weeks. Subjects will receive their first dose of study medication on Day 1 in the clinic.

Thereafter, subjects will return to the clinic at Weeks 4, 8 and 12. During these visits, subjects will undergo safety and efficacy assessments. ECGs will be conducted at  $T_{max}$  at hour 1.5 (± 30 minutes) at each clinic visit: See Table 1 for visit schedule and procedures for all assessments.

Throughout the Treatment Phase, safety parameters will be assessed and concomitant medications will also be documented. An independent safety monitor will review the data on a regular basis during the Treatment Phase.

### 6.1.2.1. Pharmacokinetics

The first 6 subjects who are eligible to be dosed will stay at the clinic overnight or return to the clinic the following day for last/final blood draw. Blood samples for MN-001/002 serum concentration will be collected at the following timepoints:

- Day 1 (Baseline): prior to the first dose
- Post dose hour 0.5, 1.5, 3, 6, 9, 12, 24\* (\*Day2)

PK parameters will be calculated and reviewed prior to increasing the dose to 250 mg bid (500 mg/d) after Week 4.

# 6.1.3. Follow-up Phase

All subjects who complete the study will return for their final visit at Week 13 for safety assessments and to assess adverse event status and document concomitant medications.

# 7. SELECTION AND WITHDRAWAL OF SUBJECTS

# 7.1. Clinical Trial Population

The population for this trial will include male and female subjects  $\geq 18$  years of age with elevated serum triglycerides and a diagnosis of NASH by liver biopsy or NAFLD confirmed by abdominal ultrasound.

# 7.2. Inclusion/Exclusion Criteria

### 7.2.1. Inclusion Criteria

- Written informed consent is obtained and willing and able to comply with the protocol in the opinion of the Investigator.
- Male or female subjects  $\geq 18$  years of age
- Histologically proven NASH (NAFLD activity score of 3 or greater with at least 1 point being ballooning) based on liver biopsy performed within the last 36 months or NAFLD confirmed by imaging studies.
- Fasting serum triglyceride level > 150 mg/dL (confirmed at screening)
- Serum ALT, AST, ALP and total bilirubin levels at Screening (- 120 days to -30 days) and Lab Visit values (- 1 week ± 5 days) are stable or changes at the Lab visit are < 20% of the values from Screening.
- Subjects on the following medications can be enrolled if these medications are necessary, cannot be stopped, and the dose has been stable for 4 months or more prior to baseline:
  - Stable doses of anti-diabetic medications
  - Stable doses of fibrates, statins, niacin, ezetimibe.
  - Stable doses of Vitamin E for at least 8 weeks
- Less than 21 units of alcohol/week for men and 14 units of alcohol/week for women over a 2-year time frame
- Females of child-bearing potential must have a negative serum ß-hCG at screening and must be willing to use appropriate contraception (as defined by the investigator) for the duration of study treatment and 30 days after the last dose of study treatment.
- Males should practice contraception as follows: condom use and contraception by female partner.
- Subject is in good physical health on the basis of medical history, physical examination, and laboratory screening, as defined by the investigator.
- Subject is willing and able to comply with the protocol assessments and visits, in the opinion of the study nurse/coordinator and the Investigator.

# 7.2.2. Exclusion Criteria

- Diagnosis of other known cause of liver disease (autoimmune, viral, genetic, drug- or alcohol-induced, or storage disease)
- Decompensated or severe liver disease defined by one or more of the following:
  - biopsy-proven cirrhosis
  - INR >1.5
  - Total bilirubin (TBL) > 1.5 x ULN, or > 2 x ULN for unconjugated bilirubin
  - serum albumin <2.8 g/dL
  - ALT or  $AST > 10 \times ULN$
  - evidence of portal hypertension including splenomegaly, ascites, encephalopathy and/or esophageal varices
- Current diagnosis of hepatocellular carcinoma (HCC) or suspicion of HCC clinically or on ultrasound
- Uncontrolled diabetes mellitus Type 2
- History of bariatric surgery
- Greater than 10-pound weight gain or loss in the last 6 months
- Clinically significant cardiovascular/cerebrovascular disease, including myocardial infarct within last 6 months, coronary artery intervention, coronary artery bypass, unstable ischemic heart disease, heart failure class III or IV, angina or cerebral vascular accident.
- Resting pulse < 50 bpm, SA or AV block, uncontrolled hypertension, or QTcF > 450 ms
- History of stomach or intestinal surgery or any other condition that could interfere with or is judged by the Investigator to interfere with absorption, distribution, metabolism, or excretion of study drug.
- Any significant laboratory abnormality which, in the opinion of the Investigator, may put the subject at risk
- History of malignancy < 5 years prior to signing the informed consent, except for adequately treated basal cell or squamous cell skin cancer or *in situ* cervical cancer.
- History of HIV (human immunodeficiency virus), HBV, HCV (cured HCV is not excluded), EBV CMV or other active infection.
- Currently has a clinically significant medical condition including the following: neurological, psychiatric, metabolic, immunologic, hematological, pulmonary, cardiovascular (including uncontrolled hypertension), gastrointestinal, urological disorder, or central nervous system (CNS) infection that would pose a risk to the subject if they were to participate in the study or that might confound the results of the study.

*Note*: Active medical conditions that are minor or well-controlled are not exclusionary if, in the judgment of the Investigator, they do not affect risk to the subject or the study results. In cases in which the impact of the condition upon risk to the subject or study results is unclear, the Medical Safety Monitor should be consulted.

- CYP2C8 substrates with a narrow therapeutic index (e.g., paclitaxel) within 15 days prior to study and throughout the study are prohibited.
- CYP2C9 substrate with narrow therapeutic index (e.g., phenytoin, S-warfarin, tolbutamide) within 15 days prior to study and throughout the study are prohibited.
- Macrolide or quinolone class antibiotics within 15 days of Screening Visit and throughout the study are prohibited.
- Steroids within 30 days prior to study drug dosing and throughout the study unless administered for a short-term treatment course during the study are prohibited.
- History of alcohol or substance abuse (DSM-IV-TR criteria) within 3 months prior to screening or alcohol or substance dependence (DSM-IV-TR criteria) within 12 months prior to screening. The only exceptions include caffeine or nicotine abuse/dependence.
- Poor peripheral venous access that will limit the ability to draw blood as judged by the Investigator.
- Currently participating, or has participated in, a study with an investigational or marketed compound or device within 3 months prior to signing the informed consent.
- Unable to cooperate with any study procedures, unlikely to adhere to the study procedures and keep appointments, in the opinion of the Investigator, or was planning to relocate during the study.

# 7.3. Subject Withdrawal/Discontinuation Criteria

Subjects may request to be withdrawn from the study at any time for any reason.

The Investigator may interrupt the treatment of any subject whose health or well-being may be compromised by continuation in the study. The following instances require subjects to be withdrawn from the study:

- Subject fails to adequately comply with the dosing, evaluations, or other requirements of the study at the discretion of Investigator.
- Subjects who have adverse events or abnormal laboratory tests that require discontinuation of study medication;
- Subjects who, in the opinion of the Investigator, should be discontinued for their wellbeing;
- Subjects who are no longer able to understand task instructions or to perform tests adequately.
- Subject becomes pregnant during the study. See section 12.7 for reporting requirements and follow-up of the pregnancy.

If a subject withdraws or is removed from the study for any reason, the reason and date of discontinuation of study medication should be recorded in the appropriate section of the Case Report Form (CRF). At the time of study discontinuation, every effort should be made to ensure all Early Termination (ET) procedures and evaluations are performed.

The study sponsors reserve the right to discontinue the study at any time for medical or administrative reasons.

# 7.3.1. Individual Stopping Criteria

Subjects who experience an adverse event of Grade 2 nausea and/or diarrhea for greater than 3 consecutive days, or Grade 3 nausea and/or vomiting for greater than 1 day thought to be related to study drug will be discontinued from the study. Additionally, subjects who experience an adverse event of Grade 3 abdominal pain lasting for greater than 1 day thought to be related to study drug will be discontinued from the study.

Subjects with abnormal laboratory tests should be discontinued or study drug temporarily interrupted. Please see section 8.6.2 and 8.6.3 for details.

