# Individual Stopping Criteria

Subjects who experience an adverse event of Grade 2 nausea and/or diarrhea for greater than 3 consecutive days or Grade 3 nausea and/or vomiting for greater than 1 day thought to be related to study drug will be discontinued from the study. Additionally, subjects who experience an adverse event of Grade 3 abdominal pain lasting for greater than 1 day thought to be related to study drug will be discontinued from the study.

Additionally, study drug will be discontinued or temporarily interrupted under the following

conditions:

- When the baseline values were <2X ULN, discontinue if ALT or AST increases to >5X baseline value (BLM).
- When the baseline values were  $\geq$ 2X ULN but <5X ULN, discontinue if ALT or AST

increases to >3X BLM

- When the baseline values were  $\geq$ 5X ULN, discontinue if ALT or AST increases to >2X BLM
- Discontinue if ALT or AST increase >2X BLM AND the increase is accompanied by a concomitant total bilirubin (TBL) increase to >2X BLM OR the INR concomitantly increases by >0.2

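### The individual GI stopping rule leaves diarrhea out of its Grade 3, more-than-1-day clause, so short related Grade 3 diarrhea has no automatic stop (low priority, cheap to close)

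*Combined protocol and SAP*

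**What the plan says.** Section 7.3.1 (Individual Stopping Criteria) requires discontinuation for "Grade 2 nausea and/or diarrhea for greater than 3 consecutive days, or Grade 3 nausea and/or vomiting for greater than 1 day" when the event is thought to be drug-related. A second sentence adds "Grade 3 abdominal pain lasting for greater than 1 day thought to be related to study drug". The synopsis carries the same rule: "Grade 2 nausea and/or diarrhea for greater than 3 consecutive days or Grade 3 nausea and/or vomiting for greater than 1 day".

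No other provision sets a Grade 3 diarrhea threshold:

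- Section 7.3 requires withdrawal for adverse events that call for stopping study medication, and lists "Subjects who, in the opinion of the Investigator, should be discontinued for their wellbeing". It gives no grade or duration.
- Section 7.3.2 stops the study after two related Grade 4 events.
- Sections 8.6.2 and 8.6.3 concern laboratory values only.
- The synopsis and section 6.1.2 provide for an independent safety monitor during treatment, again without a threshold.

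**The concern.** A graded stopping rule should become no more lenient as an event becomes more severe. This one does so for diarrhea. Read literally, four days of Grade 2 diarrhea force a stop and Grade 3 diarrhea never does. Even if Grade 2 is taken as a floor, a related Grade 3 episode of two or three days forces no stop, while the same grade and duration of nausea, vomiting or abdominal pain does.

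Diarrhea is also the characteristic adverse event of this drug. Section 4.2.1 reports it as the most frequent treatment-emergent event on MN-001 in MN-001-CL-002, above placebo in both dose groups. In the Phase 3 study it occurred in 9% and 21% of the two MN-001 groups. In MN-001-CL-001 diarrhea, nausea and vomiting were the most frequent events, and "Each of these individual events occurred in less than 10% (with only diarrhea exceeding 5%) of all MN-001-treated subjects".

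What is at stake is a uniform safety threshold across the sites of an open-label study. No efficacy endpoint definition or planned analysis depends on it.

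**Working it through.** **The rule, symptom by symptom (sections 7.3.1 and synopsis, related events)**

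| Symptom | Grade 2, more than 3 consecutive days | Grade 3, more than 1 day |
|---|---|---|
| Nausea | stop | stop |
| Vomiting | none | stop |
| Abdominal pain | none | stop (own sentence) |
| Diarrhea | stop | none |

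**Two readings of the Grade 2 clause**

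1. As a floor (Grade 2 or worse): Grade 3 diarrhea stops only after more than 3 days. More than 1 and up to 3 days is uncovered.
2. Literally (Grade 2 only): Grade 3 diarrhea of any duration is uncovered. Section 12.2.1 makes this reading matter, because a change of grade is recorded as a new event. Two days at Grade 2 followed by two at Grade 3 could appear as two 2-day events, neither longer than 3 days.

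**How many subjects could be affected**

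The plan gives no figure to reproduce. The nearest severity data are from MN-001-CL-001 (section 4.2.1): "No severe gastrointestinal AEs were reported, and none led to discontinuation from the study".

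- Denominator, from Table 3 ("placebo N=37, 500mg tid N=37, 750mg bid N=37, 750mg qd N=36"): 37 + 37 + 36 = 110 on MN-001. Check against section 4.2.1, which reports gastrointestinal events in 18.2% on MN-001 and 10.8% on placebo: 20/110 = 18.2% and 4/37 = 10.8%.
- One-sided 95% upper limit for 0 of 110: 1 - 0.05^(1/110) = 0.0269, or 2.7%.
- Expected count at that limit: 40 x 0.0269 = 1.1 (protocol sample size); 20 x 0.0269 = 0.5 (SAP section 8.1).
- Spread of the count at that rate, binomial with n = 40: P(X ≤ 2) = 0.91 and P(X ≤ 3) = 0.98, so the 95th percentile is 3.

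The 2.7% bounds a broader event than the uncovered one, which must also be diarrhea, drug-related and longer than 1 day.

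**Any-grade diarrhea, for context only**

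- MN-001-CL-001: above 5% and below 10% of 110 means 6 to 10 subjects; 6/110 x 40 = 2.2 and 10/110 x 40 = 3.6.
- Phase 3: 0.09 x 40 = 3.6 and 0.21 x 40 = 8.4.
- Phase 1 single-dose studies (80 to 600 mg) mention only the mild form: "The most common treatment emergent adverse events (TEAEs) were mild diarrhea, sensation of borborygmus, and heavy headedness".

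**The case against.** The strongest reply is that the rule may be deliberate. It sets thresholds symptom by symptom, and vomiting and abdominal pain have no Grade 2 clause either, so diarrhea is not the only asymmetry. That is correct, and the documents do not show whether the omission is a slip or a choice. But a missing lower-grade clause only makes a rule less sensitive. A missing higher-grade clause for a symptom already listed at the lower grade makes it inconsistent with itself, and no reason is given.

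The second reply is that subjects are still protected. A reader might infer from the gap that someone with severe diarrhea would have to stay on drug. The documents do not support that. Section 7.3 makes withdrawal mandatory once the investigator judges it necessary, and also allows interruption. The safety monitor reviews data during treatment, section 8.2 allows treatment of adverse events, and diarrhea needing hospitalization is a serious event with 24-hour reporting. All of this stands and shrinks the consequence, but none of it supplies a threshold.

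Third, contact after Day 1 is a Week 2 call and visits at Weeks 4, 8 and 12. Unless the subject calls, a two- or three-day episode may be over before the site hears of it, and the added clause would then remove a recovered subject. This also stands, and belongs in the cost of the fix. It applies equally to the three symptoms that already have the clause.

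Finally, a reader might take the 9% and 21% as the number falling through the gap. They are any-grade rates at 1500 mg/day and say nothing about short Grade 3 episodes.

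**Conclusion.** The gap is real and visible in the text of both sections, but it is a low-priority improvement to a safety rule. What is lost is the automatic threshold, not the ability or duty to withdraw a subject.

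The plausible rate of the uncovered event is at most about 2.7%, an expected count of at most about 1.1 of 40 (0.5 of 20). It would be wrong to read this as no more than one subject: at that rate the count could reach 3 of 40.

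The figure rests on these assumptions:

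- *Severe* in MN-001-CL-001 corresponds to Grade 3 here. Table 5 labels Grade 3 as severe, but the earlier study's scale is not given.
- Rates carry over from 750 to 1500 mg/day for 4 weeks to 250 to 500 mg/day for 12 weeks. The lower dose would reduce them (section 4.2.1 describes an apparent dose relationship for gastrointestinal events in that study), and the longer exposure would raise them.
- Rates carry over from asthma to NASH/NAFLD patients.

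**What to change.** In section 7.3.1 and in the synopsis, reword the first sentence to cover: *Grade 2 or higher nausea and/or diarrhea lasting more than 3 consecutive days, or Grade 3 or higher nausea, vomiting and/or diarrhea lasting more than 1 day*. The words *or higher* make the floor reading explicit; adding *diarrhea* to the second clause closes the gap. Leave the abdominal pain sentence and section 7.3 as they are. The absence of a Grade 2 clause for vomiting and abdominal pain may be a choice and is not changed here.

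The cost is one sentence in two places, with the written sponsor and IRB approval that section 17.1 requires. It can wait for the next amendment. The downside is possibly one or a few extra mandatory discontinuations, some after a short episode has already resolved, with loss of those subjects' later on-treatment data in a study of 20 to 40. If the sponsor did mean to tolerate short Grade 3 diarrhea, the protocol should say so and give the reason.
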